9.2.1.2 Pharmacokinetic Similarity Assessment

For population included in PKSS, the primary PK parameters, C_{max}, AUC_{0-∞} are converted by natural logarithm to perform significance test using Mixed Model, with formulation factors as fixed effects. The PK similarity of proposed biosimilar (Test) products and reference products will be evaluated by statistical analysis method of calculating 90% CIs. And the 90% CIs of the Test/Reference GMRs have to fall in the range of 80% - 125% to demonstrate the PK similarity.

T_{max} will be compared with rank test and *p* value will be provided.

The above statistical analysis will be performed using SAS 9.4 or higher.

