Safety Assessment	
AEs, Serious adverse events (SAEs), vital signs, physical examination, laboratory test, electrocardiogram (ECG), local reactions at the injection site, concomitant therapy, etc.

Immunogenicity Assessment	Incidence and severity of immunogenicity response (ADA/Nab).
Statistical Analysis	
PK Analyses
 
PK parameters estimation will be performed with WinNonlin (Version 8.4 or higher).
 
Statistical analysis below will be performed with SAS (Version 9.4 or higher).
 
For population included in Pharmacokinetic Concentration Set (PKCS), individual and mean concentration – time profile will be generated. Descriptive statistics will be performed on the concentration data including cases, arithmetic mean, standard deviation, etc.
 
For population included in Pharmacokinetic Parameter Set (PKPS), descriptive statistics will be performed on the PK parameter data including cases, arithmetic mean, standard deviation, etc.
 
For population included in Pharmacokinetic Similarity Set (PKSS), analysis of variance and the 90% confidence interval (CI) calculation will be conducted on the ln-transformed primary PK parameters C_{max}, $AUC_{0-\infty}$. And the 90% CIs of the Test/Reference geometric mean ratios (GMRs) have to fall in the range of 80% - 125% to demonstrate the PK similarity.
 
For population included in Immunogenicity Analysis Set (IAS), data will be summarized and listed by treatment, by visit, and by treatment and visit.
 
Based on Safety Set (SS), AEs, SAEs, vital signs evaluation, physical examination, laboratory test results, ECG, local reactions at the injection site, etc. will be statistically summarized and tabulated.

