6.6.2 Randomization

During the screening period, the screening number will be assigned to identify participants (e.g., S001). The participants will be randomized on Day -1. The stratified block randomization will be adopted. Participant random No. will be "10XX". When the randomized participant withdraws from the trial, random No. will be retained and the participant won't be enrolled again regardless of the withdrawal reason and whether a treatment has been received.

The randomization schedule will be generated by statistical department (an unblinded statistician) using SAS (Version 9.4 or higher).

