9.2.4 Sensitivity Analysis

Outlier: Observation extremely discordant with the average level. Outlier may be caused by the great variability of the variables, or may be an error due to a mistake which can be treated as a missing data however the mistake should be clarified.

Sensitivity Analysis: Sensitivity analyses are a series of analyses conducted against the unexpected conditions, e.g. analysis for data with missing data filled in, subgroup analysis, analysis for a different dataset, adjustment of different covariates, etc. The sensitivity analysis result will be compared with that from the due analysis to explore the robustness of inferences. Sensitivity analysis results can be a supportive data to the main analysis, however, it cannot be the primary rational to make a conclusion.

Sensitivity analysis on the outlier or other cases can be conducted, if warranted, during the PK similarity analysis. Influence of outliers can be evaluated by comparing the assessment results in cases with the outliers excluded or not. Reasons should be explained if different conclusions are reached.

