9.8 Sample Size Determination

Based on literature information ^[3], it is estimated that the inter-subject coefficient of variation of the primary PK parameters is approximately 44%. α is set to be 0.05; the power of detecting the PK similarity of the proposed biosimilar / reference product is 90%, the T/R GMR is assumed to be 1.05, the equivalent threshold is 0.80~1.25, taking risk of drop-out into account (approximately 15%), 238 participants are to be enrolled in the parallel trial.

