5.4.3 Pharmacokinetic Similarity Assessment

For population included in PKSS, the primary PK parameters, C_{max} , $AUC_{0-\infty}$ are converted by natural logarithm to perform significance test using Mixed Model, with formulation factors as fixed effects. The PK similarity of proposed biosimilar (Test) products and reference products will be evaluated by statistical analysis method of calculating 90% Cis. And the 90% CIs of the Test/Reference GMRs have to fall in the range of 80% - 125% to demonstrate the PK similarity.

T_{max} will be compared with rank test and p value will be provided.

The above statistical analysis will be performed using SAS 9.4 or higher.

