5.4.4 Sensitivity Analysis

Outlier: Observation extremely discordant with the average level. Outlier may be

caused by the great variability of the variables, or may be an error due to a mistake which can be treated as a missing data however the mistake should be clarified.

Sensitivity Analysis: Sensitivity analyses are a series of analyses conducted against the unexpected conditions, e.g. analysis for data with missing data filled in, subgroup analysis, analysis for a different dataset, adjustment of different covariates, etc. The sensitivity analysis result will be compared with that from the due analysis to explore the robustness of inferences. Sensitivity analysis results can be a supportive data to the main analysis, however, it cannot be the primary rational to make a conclusion.

The sensitivity analysis method is the same as the pharmacokinetic similarity method.

Sensitivity analysis on the outlier or other cases can be conducted, if warranted, during the PK similarity analysis. Influence of outliers can be evaluated by comparing the assessment results in cases with the outliers excluded or not. Reasons should be explained if different conclusions are reached.

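### Randomisation is stratified by factors that neither document names, and the primary similarity model carries formulation only, so the 90% CIs may be wider than they need be

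*Protocol*

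**What the plan says.** - **Allocation.** Protocol 6.6.2 states "The stratified block randomization will be adopted", and SAP 1.4 repeats the sentence. Neither gives a factor, its levels or a block size. Sex, weight and BMI appear in the documents as eligibility or baseline items, never as strata.
- **Primary model.** In Protocol 9.2.1.2 the primary parameters are "converted by natural logarithm to perform significance test using Mixed Model, with formulation factors as fixed effects". SAP 5.4.3 has the same specification: "using Mixed Model, with formulation factors as fixed effects". No random effect is named.
- **Synopsis.** Protocol 1.1 describes the same analysis differently: "analysis of variance and the 90% confidence interval (CI) calculation will be conducted on the ln-transformed primary PK parameters". It lists no model terms.
- **Adjustment elsewhere.** Protocol 9.2.4 and SAP 5.4.4 mention covariates only among generic examples of sensitivity analysis ("analysis for a different dataset, adjustment of different covariates, etc"). Those analyses are optional, and the same sections say that they cannot be the main basis for a conclusion.
- **Sample size.** Protocol 9.8 and SAP 1.6 plan on an inter-subject CV of about 44%, a GMR of 1.05, limits of 0.80 to 1.25, 90% power and about 15% drop-out, giving 238 participants. Stratification is not mentioned.

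**The concern.** A trial stratifies its randomisation because the factors are thought to matter for the outcome. If they do, balancing the arms within strata reduces the true sampling error of the test-minus-reference difference. A model with formulation alone does not see that reduction. It puts the between-stratum variance into the residual, reports a standard error that is too large, and gives a CI that is too wide. Similarity is decided by whether that 90% CI lies within 80% to 125%, so any excess width costs power.

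There is also a problem of specification. With the factors unnamed, a reader cannot tell whether the model matches the allocation, how much adjustment would gain, or whether the word *stratified* is a drafting leftover. No prespecified text settles whether the strata belong in the primary model.

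**Working it through.** **Inputs from Protocol 9.8 and SAP 1.6.** CV 44%, GMR 1.05, limits 0.80 to 1.25, alpha 0.05 per side (matching the 90% CI), 15% drop-out, 1:1 allocation.

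**Assumptions, because the documents are silent.** R² from 0 to 20%; two equally likely strata; permuted blocks of 4 within stratum; drop-out at random. The 44% is read as the total between-participant CV.

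**Step 1: reproduce the plan's own figure.**
- Log-scale variance: σ² = ln(1 + 0.44²) = 0.177, so σ = 0.4207.
- Exact power of the two one-sided tests, 101 per arm, GMR 1.05: 0.8999.
- 202 / 0.85 = 237.6, which rounds up to 238. The stated total is reproduced. (Requiring strictly at least 0.90 gives 204 evaluable, power 0.9025, and 204 / 0.85 = 240.)

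**Step 2: what the stated model does.** Each participant contributes one value per parameter. With formulation as the only term, the analysis of variance and the mixed model both reduce to the two-sample t interval:
- half-width = t(0.95, 200 df) × 0.4207 × √(2/101) = 0.0978 on the log scale;
- at an observed GMR of 1.05, the 90% CI is 0.952 to 1.158.

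**Step 3: excess width.** With the strata in the model the residual SD is σ√(1 − R²), so the formulation-only CI is wider by 1/√(1 − R²) − 1. That is 0, 1.0%, 2.6%, 5.4% and 11.8% at R² of 0, 2%, 5%, 10% and 20%. With the strata in the model, the CI at an observed GMR of 1.05 would be 0.957 to 1.152 at R² 10% and 0.962 to 1.146 at R² 20%.

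**Step 4: simulation.** 238 randomised, 15% lost (about 202 evaluable), 200,000 replicates per scenario, both models fitted to every dataset. The Monte Carlo standard error of a power near 0.90 is √(0.9 × 0.1 / 200,000) = 0.0007. Power is at GMR 1.05 and boundary error at GMR 1.25, both per endpoint.

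| R² | Power, formulation only | Power, with strata | Excess CI width | Boundary error, formulation only |
|---|---|---|---|---|
| 0 | 0.900 | 0.900 | 0% | 0.050 |
| 2% | 0.901 | 0.905 | 1.0% | 0.049 |
| 5% | 0.904 | 0.912 | 2.6% | 0.046 |
| 10% | 0.910 | 0.925 | 5.4% | 0.042 |
| 20% | 0.920 | 0.948 | 11.9% | 0.036 |

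With the strata in the model, the boundary error is 0.050 throughout.

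**Step 5: analytic check.** If stratum balance were kept perfectly, the true standard error would be σ√(1 − R²)√(2/101), while the reported one stays at σ√(2/101) = 0.0592. At R² 10%:
- True standard error: 0.0592 × 0.9487 = 0.0562.
- Boundary error: Φ(−0.0978 / 0.0562) = 0.041.
- Formulation-only power: Φ((ln 1.25 − ln 1.05 − 0.0978) / 0.0562) − Φ((ln 0.80 − ln 1.05 + 0.0978) / 0.0562) = 0.913, against 0.926 with the strata.

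At R² 5% the two powers are 0.906 and 0.913; at 20% they are 0.925 and 0.949. These agree closely with the simulation. The formulation-only powers are slightly higher here because drop-out in the simulation disturbs the balance.

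**The case against.** The strongest reply is that nothing fails. On these numbers the formulation-only analysis controls its error, is conservative if anything, and holds the planned power at every R². An analysis like that is a permissible choice. The effect size also has no anchor in the documents: R² is assumed, the gain at R² of 2% to 5% is under one percentage point, and the larger figures come from the top of the assumed range. Eligibility already limits weight to at least 50 kg and BMI to 19.0 to 26.0 kg/m², which narrows one obvious candidate stratum. The factors may be recorded in the randomisation schedule, which was not available here, or there may be none. Finally, the difference between the two model names has no numerical effect.

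Most of this stands, and it limits the point. The size cannot be fixed from the documents, the inference is valid, and the difference in model names is editorial. It is also true that giving a reason before unblinding for leaving the strata out would close the documentation gap.

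It does not remove the point. A schedule held elsewhere does not put a term into the SAP model, and nothing in Protocol 9.2.4 or SAP 5.4.4 supplies one. Including the factors by which the trial already randomises costs nothing measurable when they turn out not to matter, and narrows the deciding interval when they do.

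**Conclusion.** The point holds as a recommended improvement, not as a fault that undermines the trial. Two facts are certain on the text: neither document names the stratification factors, and the primary model contains formulation only. The consequence is conditional, because strata must exist and must predict exposure.

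From the table, the power forgone per endpoint is 0.4, 0.8, 1.5 and 2.8 percentage points at R² of 2%, 5%, 10% and 20%, and none at zero. Formulation-only power stays at about 0.90 or above. At R² 20% it already captures (0.920 − 0.900) / (0.948 − 0.900), about 40%, of the available gain. The error runs in the conservative direction, so the risk of wrongly concluding similarity is not raised, and 238 participants remains right.

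These figures rest on the assumed R² range, two strata, blocks of 4, random drop-out, and the reading of 44% as a total CV. Total is the natural reading of an inter-subject CV, but the documents do not say so. If 44% were instead a residual value after adjustment, the formulation-only model would fall short of its planned power and the case for adjustment would be stronger.

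**What to change.** 1. In Protocol 6.6.2 and SAP 1.4, name the stratification factor or factors and their levels, matching the randomisation schedule.
2. In Protocol 9.2.1.2 and SAP 5.4.3, specify the primary model as ln(parameter) = formulation + randomisation stratification factor(s), all fixed effects and no random effect. Back-transform the T/R GMR and its 90% CI from the difference in adjusted least-squares means. Use the same model description in the synopsis.
3. Keep the formulation-only model as a named sensitivity analysis.
4. If the schedule has no strata, delete the word *stratified* from Protocol 6.6.2 and SAP 1.4 and leave the model terms as they are.

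The changes should be final before database lock and unblinding; SAP section 1 already requires the SAP to be final before data lock. The cost is a few sentences and one or a few of about 200 residual degrees of freedom. At R² of zero the power is unchanged (0.900 either way). No new data are needed, and the sample size stays at 238.

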9.2.2 Handling of Intercurrent Events of Primary Estimand(s)

Not Applicable.

9.2.3 Handling of Missing Data

For missing samples before the first quantifiable sample, the concentration values will be treated as “0”. For missing samples between the two quantifiable samples or after the last quantifiable sample, the concentration values will be treated as null listed as either “Not Reportable (NR)” or “No Sample (NS)”. No value will be reported and it will be just represented as “ND” which will be treated as missing data in the table for cases that PK parameters can’t be acquired based on the concentration data. Other missing data may occur during safety assessment. Illogical data will be checked.

9.2.4 Sensitivity Analysis

Outlier: Observation extremely discordant with the average level. Outlier may be caused by the great variability of the variables, or may be an error due to a mistake which can be treated as a missing data however the mistake should be clarified.

Sensitivity Analysis: Sensitivity analyses are a series of analyses conducted against the unexpected conditions, e.g. analysis for data with missing data filled in, subgroup analysis, analysis for a different dataset, adjustment of different covariates, etc. The sensitivity analysis result will be compared with that from the due analysis to explore the robustness of inferences. Sensitivity analysis results can be a supportive data to the main analysis, however, it cannot be the primary rational to make a conclusion.

Sensitivity analysis on the outlier or other cases can be conducted, if warranted, during the PK similarity analysis. Influence of outliers can be evaluated by comparing the assessment results in cases with the outliers excluded or not. Reasons should be explained if different conclusions are reached.

9.2.5 Supplementary Analysis

Not Applicable.

9.2.6 Elimination Criteria

The principal investigator, sponsor and statisticians need to work together to decide the participant(s) to be excluded or not from relevant datasets before the statistical analysis. The judgement should be based on the degree of completion of the trial and withdrawal reasons. The relevant notes for data inclusion/exclusion should be recorded. Conditions in which data should be excluded can be as follows (not limited to):

- 1) Data of participants who don't meet the inclusion criteria or meet the exclusion criteria, which may affect the results;

- 2) Data of participants who are incompliant with the clinical protocol during the trial, which should be judged rationally according to the severity of protocol deviations;
- 3) Data of participants with other behavior which may affect pharmacokinetics results during the trial;
- 4) After taking investigational product, the data of individual participants will be excluded from PK similarity analysis (PKSS) on condition that:
 - a. Participants who have positive results of ADA at baseline (0 h);
 - b. The first postdose sample provides C_{max} values;
 - c. The pre-dose (0 h) sample provides a quantifiable concentration value;
 - d. Concomitant medication occur during the trial and there is clear evidence that the combination medication has an effect on the pharmacokinetics (PK) of the investigational products.

9.3 Analysis Supporting Secondary Objective(s)

Safety assessment of the proposed biosimilar and reference products will be one of the secondary objectives. Analyses to support the safety assessment are shown in Section 9.5.

Immunogenicity analysis, another secondary objective:

For population included in Immunogenicity Analysis Set (IAS), data will be summarized and listed by treatment, by visit, and by treatment and visit.

Statistical analysis of safety and immunogenicity data will be performed with SAS (Version 9.4 or higher).

9.4 Analysis of Exploratory Objective(s)

Not Applicable.

9.5 Safety Analyses

Based on Safety Set (SS), statistical analysis will be conducted on the safety data. AEs, SAEs, vital signs, physical examination, laboratory test results, ECG, local reactions at the injection site, concomitant therapy, etc. will be statistically summarized and tabulated.

Statistical analysis of safety data will be performed with SAS (Version 9.4 or higher).

9.6 Other Analyses

9.6.1 Demographics/Other Baseline Characteristics

Demographic and baseline characteristics will be summarized for all participants included into FAS.

For age, weight, height and BMI: the cases, arithmetic mean, standard deviation, median, quartile, min and max will be statistically summarized.

For gender, nation, race: the cases and percentage will be statistically summarized.

For medical history, surgical history: classification according to MedDRA (Version 27.0 or higher) and the cases and percentage will be statistically summarized.

For smoking/alcohol/allergy/drug abuse history, viral tests, alcohol breath tests and drug abuse tests, antinuclear antibody tests, tuberculosis diagnosis as well as chest X-ray: the cases and percentage will be statistically summarized.

Prior and concomitant medications will be coded using the World Health Organization (WHO)-Drug, and listed by reported term / preferred term and Anatomical Therapeutic Class classification. All prior / concomitant medications, concomitant medications / non-drug therapy taken by participant included into FAS will be listed and statistically summarized with cases and percentage.

9.7 Interim Analyses

Not Applicable.

9.8 Sample Size Determination

Based on literature information ^[3], it is estimated that the inter-subject coefficient of variation of the primary PK parameters is approximately 44%. α is set to be 0.05; the power of detecting the PK similarity of the proposed biosimilar / reference product is 90%, the T/R GMR is assumed to be 1.05, the equivalent threshold is 0.80~1.25, taking risk of drop-out into account (approximately 15%), 238 participants are to be enrolled in the parallel trial.

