3.2 Associated Endpoint and Estimand

PK Endpoints

The primary PK endpoints are the maximum serum drug concentration (C_{max}) and areas under the serum concentration versus time curve extrapolated to infinity ($AUC_{0-\infty}$).

The secondary pharmacokinetic endpoints are areas under the serum concentration versus time curve calculated to the last measurable observation (AUC_{0-t}) and to 65 days postdose ($AUC_{0-65days}$), the time to maximum serum concentration (observed) (T_{max}), the elimination half-life ($t_{1/2}$) and terminal elimination rate constant (K_{el}), apparent distribution volume (V_d/F) and clearance (CL/F).

Safety Estimands

AEs, Serious adverse events (SAEs), vital signs, physical examination, laboratory test, electrocardiogram (ECG), local reactions at the injection site, concomitant therapy, *etc.*

Immunogenicity Estimands

Incidence and severity of immunogenicity response (ADA/Nab).

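### The stated 90% power is for one endpoint; the similarity decision needs both Cmax and AUC0-∞ to pass, and its power is lower

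*Protocol*

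**What the plan says.** Protocol 9.8 gives one set of planning values, which SAP 1.6 repeats:

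- Variability: "it is estimated that the inter-subject coefficient of variation of the primary PK parameters is approximately 44"%, taken from one cited literature source.
- Test level: "α is set to be 0.05".
- Power and ratio: "the power of detecting the PK similarity of the proposed biosimilar / reference product is 90%, the T/R GMR is assumed to be 1.05".
- Limits: "the equivalent threshold is 0.80~1.25".
- Drop-out of about 15% and 238 enrolled, randomised 1:1.

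Protocol 3.2 names two primary PK endpoints, Cmax and AUC0-∞. For these log-transformed parameters, Protocol 9.2.1.2 and SAP 5.4.3 set the decision rule: "the 90% CIs of the Test/Reference GMRs have to fall in the range of 80% - 125% to demonstrate the PK similarity". The synopsis (Protocol 1.1) says the same. Neither document says whether the 90% is per endpoint or joint, whether each parameter has its own CV, or what correlation is expected between them.

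**The concern.** The 90% is attached to the similarity conclusion itself. The rule refers to the CIs, in the plural, of the two primary parameters, and its natural reading is that each must lie within 80–125%. The power to pass two tests cannot exceed the power to pass the harder one. When both have the same power, it is strictly lower unless the two log parameters are perfectly correlated. If 238 came from a calculation for one endpoint, the stated power overstates the chance that the trial reaches its conclusion.

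What is at stake is the sponsor's planning risk, meaning the chance that products with a true GMR of 1.05 fail to show similarity. Requiring both endpoints to pass does not inflate type I error, so the validity of a positive result is not in question.

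**Working it through.** **Inputs.** From Protocol 9.8: CV 44%, GMR 1.05, limits 0.80–1.25, α 0.05 (one-sided for each test, which matches a 90% CI), 15% loss, 238 enrolled. From Protocol 4.1: 1:1 parallel groups. Assumed: the correlation ρ between log Cmax and log AUC0-∞.

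**Step 1: reproduce 238 with one endpoint.**

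- Log-scale SD: σ = √ln(1 + 0.44²) = 0.4207.
- Evaluable: 238 × 0.85 = 202.3, so 101 per arm.
- SE = 0.4207 × √(2/101) = 0.0592; df = 200; t(0.95) = 1.6525.
- Upper limit: (ln 1.25 − ln 1.05)/SE − t = 0.1744/0.0592 − 1.6525 ≈ 1.293; Φ ≈ 0.902.
- Lower limit: (ln 1.05 − ln 0.80)/SE − t = 0.2719/0.0592 − 1.6525 ≈ 2.941; Φ ≈ 0.998.
- Approximate power = 0.902 + 0.998 − 1 ≈ 0.90.

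Integrating exactly over the distribution of the pooled variance gives 0.8972 at 100 per arm, 0.8999 at 101 and 0.9025 at 102. Then 202/0.85 = 237.6, rounded up to 238. A strict 0.9000 needs 102 per arm and 204/0.85 = 240 enrolled, so 238 matches to rounding. Two alternative readings do not lead to 238: using 0.44 directly as the log SD gives 222 evaluable (262 enrolled), and 2.5% per side gives 248 evaluable.

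**Step 2: apply the two-endpoint rule.** Joint power was simulated with 1,000,000 trials per cell (Monte Carlo SE about 0.0004), using bivariate normal log-mean differences and a Wishart pooled covariance. CV is 44% and GMR 1.05 for both endpoints.

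| Assumed ρ | 101 per arm (15% lost) | 119 per arm (none lost) |
|---|---|---|
| 0 | 0.81 | 0.88 |
| 0.5 | 0.83 | 0.89 |
| 0.7 | 0.85 | 0.90 |
| 0.8 | 0.86 | 0.91 |
| 0.9 | 0.87 | 0.92 |
| 0.95 | 0.88 | 0.92 |
| 1 | 0.90 | 0.94 |

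The first row can be checked by hand: 0.8999² = 0.81 and 0.9381² = 0.88. Zero correlation is implausible for two measures of the same curve, so that row is only an outer bound.

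**Step 3: vary what the documents leave open (101 per arm).**

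| Change | Joint power, ρ from 0 to 0.95 |
|---|---|
| Second CV 40% | 0.85–0.89 |
| Second CV 35% | 0.88–0.90 |
| Second CV 30% | 0.895–0.90 |
| One GMR 1.00, both CVs 44% | 0.87–0.88 |

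If the GMRs lie on opposite sides of 1 (1.05 and 1/1.05) with both CVs 44%, joint power is about 0.80–0.81 for ρ from 0 to 0.9.

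**The case against.** The strongest reply is that nothing is miscalculated. The 238 is reproduced, quoting power per endpoint is common, and the documents simply do not say which is meant. The size of any shortfall depends on two things they do not give: the correlation, and whether 44% is common to both parameters or the larger of two CVs. On the figures above, a second CV of 30% leaves a gap of at most half a percentage point.

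Loss may also fall unequally. Entry to the similarity set needs only one evaluable PK parameter (Protocol 9.1, SAP section 3), and a late drop-out could lose AUC0-∞ but keep Cmax. In the outer case, with 119 per arm for Cmax, 101 for AUC0-∞ and both CVs 44%, joint power is 0.859, 0.869 and 0.880 at ρ 0.5, 0.7 and 0.9 (400,000 simulations, with sample variances drawn independently as an approximation). With a Cmax CV of 35% it is 0.894–0.899. Finally, both the one-endpoint basis of 238 and the rule that both must pass are inferences; the documents do not use the word both or co-primary.

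Much of this stands as a limit on the size. It does not remove the point. The text ties 90% to the similarity conclusion and gives one CV and one GMR for the primary parameters together. On those terms, with the plan's own 15% loss, joint power is below 90% for any correlation under 1, and the unequal-loss case with both CVs at 44% is still below it. No rule by which one endpoint would suffice appears anywhere.

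**Conclusion.** The concern holds. The stated 90% is the power for one endpoint and is presented as the power for a decision that needs two. With CV 44% and GMR 1.05 for both and about 202 evaluable, joint power is about 0.83–0.87 for assumed correlations of 0.5–0.9. The chance of failing at that GMR is then about 13–17% instead of 10%.

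The direction is firm under those conditions. The size is not: it shrinks to almost nothing if the second CV is about 30%, and with no drop-out joint power reaches 0.90 at a correlation of about 0.7. As written, the stated power cannot be checked against the rule it is meant to describe. This is a planning and reporting fault that should be corrected; it does not affect type I error.

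**What to change.** In Protocol 9.8 and SAP 1.6:

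1. State that 238 enrolled, about 202 evaluable (101 per arm), gives 90% power for each primary endpoint separately at CV 44% and GMR 1.05.
2. State the CV used for Cmax and the CV used for AUC0-∞. If they differ, give each endpoint's power at its own CV.
3. State that both endpoints must pass, and give the joint power with the correlation assumed. For example: about 85% if the log parameters correlate at 0.7 and both CVs are 44%. The sponsor should put in its own justified correlation, or show a range.

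The cost is about two sentences in each of two sections, and a slightly less favourable power for the overall decision. Enrolment, analysis and decision rule do not change.
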